**Impact of the PCSK9 Inhibitor Evolocumab on the Pharmacodynamic Effects of
Clopidogrel in Patients with Atherosclerotic Cardiovascular Disease and
High or Normal On-Treatment Platelet Reactivity**

[name], PhD
University of Florida College of Medicine-Jacksonville
[name]
[name]
[contact]
[contact]
E-mail: [contact]

Background and Significance

Dual antiplatelet therapy (DAPT) with aspirin and a P2Y₁₂ receptor inhibitor represents the standard of care for the long-term secondary prevention of atherothrombotic events in patients with acute coronary syndrome (ACS) or undergoing percutaneous coronary intervention (PCI) [1]. Moreover antiplatelet therapy is commonly used in patients with other atherothrombotic disease manifestations, such as stroke and peripheral arterial disease (PAD). Clopidogrel is the most widely used P2Y₁₂ receptor inhibitor and is the only agent of this class currently recommended in patients with stable coronary artery disease (CAD) undergoing PCI, and for the treatment of stroke or PAD [2]. Although the efficacy of DAPT with aspirin and clopidogrel has been consistently shown in different clinical settings, rates of ischemic recurrences remain elevated despite this treatment regimen, especially in high risk patients [1,3]. This has been in part attributed to the high interindividual variability in responses to clopidogrel [3,4]. Clopidogrel is a pro-drug which requires a two-step metabolic transformation to exert its antiplatelet effect. Pharmacodynamic (PD) studies have shown that approximately 30-40% of patients experience high on-treatment platelet reactivity (HPR) while receiving clopidogrel treatment [3,4]. Importantly HPR status has been strongly associated with an increased risk of ischemic events, in particular stent thrombosis, in patients with ACS and following PCI [4]. This underscores the need for strategies aimed to reduce HPR rates in patients treated with clopidogrel. Several factors (clinical, cellular, and genetic) have been associated with HPR on clopidogrel [3,4]. Among these, genetic polymorphisms of the hepatic cytochrome P450 (CYP) 2C19 gene, the enzyme involved in both metabolic steps of transformation of clopidogrel pro-drug into its active metabolite, have shown to affect clopidogrel PD and pharmacokinetic and impact clinical outcomes [3,4]. In particular, the *2 and *3 loss-of-function

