is simply due to LDL reduction or might be related to other mechanisms is currently subject of investigation. Although LDL reduction with statin therapies has been associated with reduction in platelet reactivity, to date the effects on platelet aggregation of adjunctive lipid lowering with evolocumab has not been explored.

Study aims

The primary aim of the present study is to investigate the effects of evolocumab in addition to statin therapy on platelet reactivity in patients with atherosclerotic cardiovascular disease (ASCVD) while on clopidogrel treatment. Secondary aims will include the effects on cholesterol levels.

Research Plan

Study Population

Inclusion criteria:

1. Patients with ASCVD, defined as prior ACS, history of myocardial infarction, stable or unstable angina, coronary or other arterial revascularization, stroke, transient ischemic attack, or PAD presumed to be of atherosclerotic origin.
2. On therapy with clopidogrel (75mg od), with or without low-dose aspirin (81mg od), as per standard-of-care for at least 30 days.
3. HPR, defined as P2Y₁₂ reaction units (PRU) > 208 by VerifyNow P2Y₁₂, or normal platelet reactivity (NPR), defined as PRU between 85 and 208.

4. Fasting LDL-cholesterol ≥ 70 mg/dL or a non-high-density lipoprotein cholesterol (HDL-C) of ≥ 100 mg/dL after ≥ 2 weeks of optimized stable lipid-lowering therapy with maximally tolerated dose of statin, which would ideally include a high-intensity statin, but must be at least moderate intensity statin (i.e. atorvastatin 20 mg or equivalent, with or without ezetimibe. Maximal tolerated dose will be defined based on patient clinical history (no statin re-challenge will be performed).
5. Age ≥ 18 years old.

[figure not shown]
Exclusion criteria:

1. On treatment with any oral anticoagulant (vitamin K antagonists, dabigatran, rivaroxaban, apixaban, edoxaban).
2. On treatment with any antiplatelet agent other than aspirin and clopidogrel in the past 14 days.
3. Use of PCSK9 inhibitors in the past 90 days
4. Creatinine clearance < 30 mL/minute.
5. Known severe hepatic impairment.
6. History of a serious hypersensitivity reaction to evolocumab
7. Hemodynamic instability
8. Pregnant and breastfeeding women [women of childbearing age must use reliable birth control (i.e. oral contraceptives) while participating in the study].

Research Design

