The proposed investigation will be a prospective, randomized, parallel-design, double-blind, placebo-controlled, PD study conducted in patients with ASCVD and HPR (PRU>208) or NPR (PRU 85-208) on clopidogrel. Patients with low platelet reactivity (PRU<85) will be excluded given that their distribution profile of platelet reactivity would be unlikely to unravel a platelet inhibitory treatment effect of evolucumab. The study will be performed at the University of Florida Health Science Center at UF Health Jacksonville - Division of Cardiology. Patients will be recruited in the Cardiology Clinics of our institution and will be screened by Cardiology Research staff, who will verify that all candidates meet inclusion and exclusion criteria. Results from blood tests performed within the last 90 days will be considered valid for screening purposes. If these are not available, a blood sample will be collected for the screening phase.

After providing written informed consent, patients meeting study entry criteria will be randomly assigned to receive either evolucumab 420 mg s.c. or placebo (0.9% sodium chloride s.c. injection). Blood sampling for PD testing will be conducted at 3 time-points: baseline, and 14±2 days and 30±2 days after randomized drug administration. At each time point, blood will be collected before the morning dose of clopidogrel, in order to measure trough levels of platelet inhibition. During study treatment major adverse cardiac events (death, MI, stroke, and urgent revascularization procedures) and serious adverse events (bleeding and other adverse events) will be collected. A flow diagram of the study design is illustrated below.

Laboratory testing

PD testing

Peripheral venous blood samples will be drawn through a short venous catheter inserted into a forearm vein and collected in citrate, EDTA, and serum tubes as appropriate for assessments. The first 2-4 mL of blood will be discarded to avoid spontaneous platelet activation. Blood sampling will be performed at 3 time points as indicated above in the study design section. Various PD assays will be performed as described below:

1. VerifyNow P2Y12
2. Light transmittance aggregometry (LTA)
3. Thrombelastograph Coagulation Analyzer TEG 6s Series system (CORAX[®] system)

Description of laboratory assays

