1) VerifyNow (VN) P2Y12: The VerifyNow System is a turbidimetric based optical detection system which measures platelet induced aggregation as an increase in light transmittance (Accumetrics, San Diego, CA) and will be utilized according to manufacturer's instructions, as previously described [14]. The assay is based on microbead agglutination and uses specific reagents for the pathways of interest. The VN-P2Y12 assay, by combining ADP+PGE1, measures changes in

platelet function specific to P2Y₁₂ receptor inhibitors. The assay is based upon the ability of activated platelets to bind fibrinogen. Fibrinogen-coated microparticles aggregate in proportion to the number of GP IIb/IIIa receptors expressed. Microbead aggregation is more rapid and reproducible if platelets are activated; therefore the reagents are incorporated into the assay channel to induce platelet activation without fibrin formation. Light transmittance increases as activated platelets bind and aggregate fibrinogen-coated beads. The instrument measures this change in optical signal and reports results in P2Y₁₂ Reaction Units (PRU). HPR will be defined as PRU > 208 and NPR as PRU 85-208 [4].

2) Light transmittance aggregometry (LTA): Platelet aggregation will be performed using LTA according to standard protocols. Blood will be collected in citrated (3.2%) tubes. LTA will be assessed using platelet rich plasma (PRP) by the turbidimetric method in a 2-channel aggregometer (Chrono-Log 490 Model, Chrono-Log Corp., Havertown) as previously described [14]. Platelet agonists will include arachidonic acid (AA, 1 mM), collagen (3 µg/ml), ADP (5 and 20 µM), TRAP (15 µM). PRP will be obtained as a supernatant after centrifugation of citrated blood at 1000 rpm for 10 minutes. The isolated PRP will be kept at 37° C before use. Platelet poor plasma (PPP) will be obtained by a second centrifugation of the blood fraction at 2800 rpm for 10 minutes. Light transmission will be adjusted to 0% with the PRP and to 100% for the PPP for each measurement. Curves will be recorded for 6 minutes and platelet aggregation will be determined as the maximal percent change (MPA) in light transmittance from baseline using PPP as a reference. HPR will be defined as MPA with 20 µM ADP > 59% and MPA with 5 µM ADP > 46% [4].

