
network as the foundation, additional clot strength due to platelet-fibrin bonding related to ADP and AA platelet receptor activation can be measured. The HKH reagent, a combination of kaolin and heparinase, generates test data for the uninhibited MA resulting from thrombin activation of the blood sample, while the heparinase neutralizes the effects of heparin. The HKH test provides measures of R (Reaction time; the amount of time between the start of the test and the beginning of coagulation), K (the speed of formation of the clot from R time to a specific clot strength), Angle (the speed of clot strengthening), LY30 (Percent lysis 30 minutes after MA is finalized) and MA parameters; The activatorF test provides the contribution of fibrin to the overall strength of the clot. This test value is used in the calculation of aggregation/inhibition for MA ADP and MA AA. The AA and ADP test provide measures of MA, percent inhibition and percent aggregation. HPR will be defined as MA ADP > 47 mm [15].

Genetic testing

Spartan RX rapid genotyping: Spartan RX (Spartan Bioscience Inc., Ontario, Canada) is the rapid genotyping system determining the CYP2C19 (*1,*2,*3,*17) allele status within 1 hour [16]. This test consists of four separate steps intended to be done in less than 8 minutes: acquisition of a buccal swab; insertion of the swab into the cartridge; insertion of the reaction solution into the device; and analysis of CYP2C19 genotype triggered by a button on the device.

Lipid profile and PCSK9 levels

Blood for the evaluation of the effects on lipids will be drawn at the same time points as described above for PD measurements. Cholesterol measures will include a standard lipid profile and lipoprotein(a) [Lp(a)], which will be measured by the central laboratory of our institution

according to standard protocols. At each time point, blood samples samples will also be stored for measurement of PCSK9 serum levels and for possible future analyses. PCSK9 levels will be measured by ELISA as previously described [17].

Study endpoints and sample size calculation

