The primary end point of our study is the reduction in platelet reactivity, as defined by PRU, between evolocumab and placebo at 30 days after randomization in each cohort. We hypothesize that evolocumab therapy will be associated with a reduction of 30 PRU in patients with HPR and NPR. The rationale for considering a reduction of 30 PRU is because this value approximates that observed with more intense lipid lower therapy using statin therapy [18]. Statistical assumptions were derived for each cohort of patients based on distribution of their PRU levels from a cohort of subjects on maintenance clopidogrel therapy (HPR: 247 ± 29 ; NPR: 150 ± 35). In patients with HPR, 17 patients per group (34 total) are needed to detect a 30 PRU difference with 80% power. In NPR patients, 23 patients per group (46 total) are needed to detect a 30 PRU difference with 80% power. Therefore, under the assumption of a 30 PRU reduction with evolocumab compared with placebo in each cohort, 80% power and α of 0.05, 80 total patients with a valid primary end point will be needed. Considering a possible dropout rate of 10%, up to 90 patients will need to be randomized. We anticipate that up to 500 patients will need to be screened to reach our sample size. Given the absence of preliminary studies exploring the effects of PCSK9 inhibitors on platelet aggregation the expected reduction in PRU was arbitrarily defined.

Other endpoints will include the comparisons between evolocumab and placebo of all PD parameters measured by multiple assays, and of cholesterol levels at each time point. Exploratory analyses will assess the differential response to evolocumab treatment according to the presence of

LOF genetic polymorphisms as well as the levels of PCSK9. We will also investigate different response profiles in patients with and without aspirin.

Statistical analysis plan

Categorical variables will be expressed as frequencies and percentages. Continuous variables will be presented as mean \pm SD or median [IQR]. An analysis of covariance (ANCOVA) method with a general linear model will be used to evaluate the primary end point as well as all between-groups comparisons of platelet reactivity, cholesterol levels and HS-CRP. The Fisher's exact test or Pearson's chi square test will be used to evaluate t comparisons of HPR and NPR rates between groups.

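### The HPR-rate test ignores baseline PRU although PRU 208 sets both entry and outcome status; adjusting for baseline recovers some power at no cost

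*Combined protocol and SAP*

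**What the plan says.** Under Inclusion criteria the HPR cohort is defined by "HPR, defined as P2Y₁₂ reaction units (PRU) > 208 by VerifyNow P2Y₁₂". The VerifyNow entry under Description of laboratory assays uses the same boundary to classify patients: "HPR will be defined as PRU > 208 and NPR as PRU 85-208". No repeat or confirming reading is described. HPR has separate definitions for light transmittance aggregometry (59% with 20 µM ADP, 46% with 5 µM) and for TEG ("HPR will be defined as MA ADP > 47 mm"), so the shared cut-off concerns VerifyNow only.

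The Statistical analysis plan section names ANCOVA for the primary end point and for the other between-group comparisons of platelet reactivity, without listing covariates. It then adds: "The Fisher's exact test or Pearson's chi square test will be used to evaluate t comparisons of HPR and NPR rates between groups". That sentence gives no visit, does not say whether the cohorts are kept apart, and leaves the choice between the two tests open.

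Under Study endpoints and sample size calculation, the primary end point is PRU at 30 days in each cohort. The HPR rate has no hypothesis and no power statement. Research Design schedules platelet testing at baseline, day 14 and day 30.

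**The concern.** A patient enters the HPR cohort because one PRU lay above 208, and stops counting as HPR when a later PRU is 208 or less. Selection on a noisy reading brings regression to the mean, so some patients will cross back in either arm without any drug effect. Whether an untreated patient crosses depends largely on how far above 208 the baseline value lay, and the trial records that value. Fisher's and Pearson's tests leave this predictable variation in the error term.

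At stake is the chance that a real effect shows up in the HPR rate. The Background and Significance section motivates the trial by the need to lower HPR rates, so readers will look for this result, and the planned cohort has only 17 patients per arm.

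**Working it through.** **1. The plan's own sample size.** Inputs from Study endpoints and sample size calculation: a 30 PRU difference, "HPR: 247 ± 29 ; NPR: 150 ± 35", 80% power, α 0.05. Normal formula: n = 2(1.960 + 0.842)² SD²/30².
- HPR, SD 29: 14.7, so 15 per group; the t-test version gives 16; the plan states 17 (t-test power 83.3%).
- NPR, SD 35: 21.4, so 22; the t-test version gives 23; the plan states 23 (t-test power 81.1%).

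The figures are reproduced to within 2 patients. They are for continuous PRU, not for the HPR rate.

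**2. Rate comparison on the plan's own cohort figures.** Suppose later PRU is normal with mean 247 and SD 29 on placebo, and mean 217 on evolocumab.
- Placebo, share at 208 or less: Φ((208 − 247)/29) = Φ(−1.345) = 9%.
- Evolocumab: Φ((208 − 217)/29) = Φ(−0.310) = 38%.
- Power with 17 per arm: Fisher 38%, chi-square 52%.

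**3. Adding regression to the mean.** The documents give no within-patient SD or test-retest correlation, so both are assumed.
- Parent population: normal, mean 160, SD 65. Cut at 208 it gives about 246 ± 31, and within 85–208 about 150 ± 33, close to the plan's figures.
- Within-patient SD σ: 15 to 35 PRU. The correlation between two readings is r = 1 − σ²/65². For σ = 15, r = 1 − 225/4225 = 0.95; for σ = 35, r = 1 − 1225/4225 = 0.71.
- The entry reading serves as baseline, and the outcome is one reading at day 30, the visit of the primary end point.

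With no drug effect, the share of the HPR cohort at 208 or less is 17% (σ = 15), 29% (25) and 41% (35). With a 30 PRU effect it is 51% at σ = 15 and 64% at σ = 35.

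**4. How far that share depends on the assumptions.** The parent in step 3 puts 1 − Φ((208 − 160)/65) = 23% of patients above 208. The background section says "approximately 30-40% of patients experience high on-treatment platelet reactivity (HPR) while receiving clopidogrel treatment". Parents matched to other figures in the documents give, for r = 0.5 / 0.7 / 0.9:
- 40% HPR prevalence: 40 / 31 / 17%.
- 30% prevalence: 48 / 36 / 21%.
- HPR mean and SD: 31 / 23 / 13%.
- HPR and NPR means: 53 / 41 / 23%.

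With step 2 as the low end, the span is about 9 to 53%.

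**5. Power, HPR cohort, 17 per arm, true effect 30 PRU, model of step 3 (simulation).**

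| Within-patient SD | 15 | 20 | 25 | 30 | 35 |
|---|---|---|---|---|---|
| Fisher | 42% | 32% | 26% | 22% | 18% |
| Chi-square | 57% | 45% | 38% | 34% | 29% |
| Linear risk difference, adjusted for baseline PRU | 69% | 55% | 43% | 36% | 29% |
| Gain over Fisher (points) | 27 | 23 | 17 | 14 | 11 |
| Gain over chi-square (points) | 12 | 10 | 5 | 2 | 0 |

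Type I error of the adjusted linear analysis was 4.3 to 5.4%. A repeat with 20,000 trials per cell agreed with every power figure to within 2 points.

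**6. Logistic alternative.** Logistic regression adjusted for baseline PRU had type I error of about 5 to 11% at this sample size.

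**The case against.** The strongest reply is that little depends on this test. The HPR rate is neither the primary end point nor powered. In the model of step 3, ANCOVA on continuous PRU with baseline as covariate has about 98/85/67/54/43% power at SD 15/20/25/30/35, more than any analysis of the rate. Part of the gain over Fisher comes simply from using chi-square, which the plan already allows, and at an SD of 30 or more adjustment adds almost nothing to chi-square. All of this stands. It limits the weight of the point but does not remove it, because the rate comparison is still planned and a covariate already collected would be left unused.

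Two stronger readings are tempting, and the documents support neither.
- A reader might infer that the shared cut-off biases the rate comparison or damages the primary analysis. Regression to the mean falls on both randomised arms alike, and simulated type I error was about 2 to 3% for Fisher and 4 to 6% for chi-square. The primary ANCOVA does not use the cut-off as an outcome.
- A reader might infer that a fall from 100% HPR within the evolocumab arm will be credited to the drug. The plan compares rates between groups and plans no such within-arm test. Nor is a 100% starting rate assured: Research Design accepts screening blood results up to 90 days old and takes a separate baseline sample.

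A rule that PRU must be 208 or less at both day 14 and day 30 also looks attractive, but it lowers the crossing rate in both arms together. Fisher power is 45/33/26/22/20% with it and 42/32/26/22/19% without. If only half the effect is present at day 14, it drops to 20/15/13/11/10%.

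**Conclusion.** The point holds as a modest, inexpensive improvement. The planned HPR-rate tests cannot use baseline PRU, and in the HPR cohort some patients will fall to 208 or below without a drug effect. The consequence is lost power on a secondary comparison, not bias.

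The size is conditional. The 17 to 41% share rests on an assumed within-patient SD of 15 to 35 PRU and one fitted parent population. The power figures also assume 17 evaluable patients per arm, a uniform 30 PRU shift, a single outcome reading at day 30 and the entry reading as baseline; the plan does not fix the visit for the rate test. Even with adjustment, power reaches at most 69% in this range, so a non-significant HPR-rate result would say little about absence of effect.

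**What to change.** In the Statistical analysis plan section, for the VerifyNow HPR rate in the HPR cohort:
- Make the main rate analysis the between-arm difference in the proportion with PRU of 208 or less, from a linear model with treatment and continuous baseline PRU, and name the visit (day 30 would match the primary end point).
- Report the crude Fisher or chi-square test as supportive.
- Do not substitute logistic adjustment unless its type I error has been checked at this sample size.

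Keep the 208 cut-off, and do not add a two-visit confirmation rule. The planned between-group wording already makes placebo the comparator and needs no addition.

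The cost is SAP wording only: no new visits, samples or patients. The return is small against chi-square if the within-patient SD is 30 PRU or more.

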A 2-tailed p value of < 0.05 will be considered to indicate a statistically significant difference for all the above analyses. Statistical analysis will be performed by our group using SPSS v22.0 software (SPSS Inc. Chicago, IL).

Publication Strategy/Additional Information

Study subjects will be identified first (months 1-24): we expect to enroll 3-4 subjects monthly and complete enrollment in 24 months (total: 90 subjects randomized). Month 25 will be implied for statistical analysis and months 26-27 for manuscript preparation. We intend to present data at a major scientific meeting at completion of the study.

Possible Discomforts and Risk

In clinical trials, the most commonly reported adverse events with evolocumab included nasopharyngitis (4.0% of evolocumab recipients vs. 3.9% of controls), arthralgia (1.8% vs. 1.6%), myalgia (2.0% vs. 1.8%), upper respiratory tract infection (2.1% vs. 2.2%), back pain (2.3% vs. 2.2%), and nausea (1.8% vs. 1.2%). Injection-site reactions were reported in 3.3% of evolocumab recipients and 3.0% of controls. Allergic reactions occurred in 5.1% and 4.7% of evolocumab-treated and placebo-treated patients, respectively. The most common allergic reactions were rash (1.0% vs. 0.5% for evolocumab and placebo, respectively), eczema (0.4% vs. 0.2%), erythema (0.4% vs. 0.2%), and urticaria (0.4% vs. 0.1%) [19].

All clinical events described above, if they were to occur, as well as death, myocardial infarction, stroke, and urgent revascularization procedure with PCI or coronary artery bypass grafting will be recorded. Clinical events will be evaluated by a local committee, comprised of 2 faculty members (2 cardiologists), not directly involved in the research. In the event of a report of a serious adverse event, the local committee will meet and treatment management will be managed according to physician recommendation.

Definition of Adverse Events

An adverse event is any unintended or undesirable experience that occurs during the course of the clinical investigation whether or not it is considered to be therapy related. This includes any newly occurring event or previous condition that has increased in severity or frequency since the initiation of study treatment. Adverse events will be followed until resolution while the patient remains on-study. Once the patient is removed from study, events thought to be related to the study therapy will be followed until resolution or until the patient starts a new treatment regimen.

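### The planned test of NPR rates cannot be read as benefit or harm when pooled or in the NPR cohort, and any overall HPR-rate test should be stratified by entry cohort

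*Combined protocol and SAP*

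**What the plan says.** The Statistical analysis plan states that Fisher's exact test or Pearson "chi square test will be used to evaluate t comparisons of HPR and NPR rates between groups". It does not say whether the two entry cohorts are pooled, separate or stratified, at which visit the rates are compared, or what decides between the two tests. The significance rule covers these tests too: "A 2-tailed p value of < 0.05 will be considered to indicate a statistically significant difference for all the above analyses".

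For VerifyNow, Description of laboratory assays says "HPR will be defined as PRU > 208 and NPR as PRU 85-208", and the inclusion criteria use the same cut-offs for entry. Patients with PRU below 85 are excluded at entry (Research Design), and no outcome category is named for patients who fall below 85 on treatment.

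Study endpoints and sample size calculation works by cohort. The primary end point is the "reduction in platelet reactivity, as defined by PRU, between evolocumab and placebo at 30 days after randomization in each cohort", and "Statistical assumptions were derived for each cohort of patients based on distribution of their PRU levels". The sizes are 17 per group (HPR) and 23 per group (NPR). On allocation, Research Design says only that "patients meeting study entry criteria will be randomly assigned to receive either evolucumab 420 mg s.c. or placebo"; stratification by cohort is not mentioned.

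**The concern.** Two features of the rate comparison need attention.

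First, NPR is a middle band. A drug that lowers PRU moves HPR-cohort patients into it and some NPR-cohort patients out of the bottom of it. Pooled, these movements oppose each other. Within the NPR cohort, a lower NPR rate could mean more patients above 208 or more below 85.

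Second, the sentence leaves room for one 2×2 table over all 80 patients. Such a table ignores each patient's starting category, which largely determines the day-30 category.

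These are secondary results, but Background and Significance motivates the work by HPR rates: "This underscores the need for strategies aimed to reduce HPR rates in patients treated with clopidogrel". Readers will look at them, and an unstated choice between pooled and per-cohort testing could be made after the data are seen.

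**Working it through.** **Inputs.** From Study endpoints and sample size calculation: HPR 247 ± 29, NPR 150 ± 35, a 30 PRU reduction in each cohort, 17/17 and 23/23, and "80% power and α of 0.05, 80 total patients with a valid primary end point will be needed". Cut-offs are 208 and 85. Tests are two-sided at 0.05.

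**The plan's sample size.** n per group = 2(1.96 + 0.842)² × (SD/30)². HPR: 15.70 × (29/30)² = 14.7, so 15. NPR: 15.70 × (35/30)² = 21.4, so 22. With the t distribution these become 16 and 23; the plan's 17 and 23 agree closely. For dropout, 80/0.9 = 88.9, so 89 against the plan's 90. The inputs are therefore read as intended. The plan states no power for rates.

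**Day-30 categories.** Assumption: day-30 PRU is normal with the plan's cohort means and SDs, shifted by 30 on evolocumab, with no regression to the mean.

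- HPR cohort, above 208: placebo 1 − Φ((208 − 247)/29) = 91.1%; evolocumab 1 − Φ((208 − 217)/29) = 62.2%.
- NPR cohort, above 208: 1 − Φ((208 − 150)/35) = 4.9%; 1 − Φ((208 − 120)/35) = 0.6%.
- NPR cohort, below 85: Φ((85 − 150)/35) = 3.2%; Φ((85 − 120)/35) = 15.9%.
- HPR cohort, below 85: effectively none.

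**NPR rate (85–208).** Power is by exact enumeration, arms balanced by cohort.

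| | Placebo | Evolocumab | Chi-square power |
|---|---|---|---|
| HPR cohort | 8.9% | 37.8% | 51.9% |
| NPR cohort | 92.0% | 83.5% | 13.8% |
| Pooled | 56.7% | 64.1% | 4.1% |

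The pooled rates are (17 × 8.9 + 23 × 92.0)/40 and (17 × 37.8 + 23 × 83.5)/40. With allocation ignoring cohort, pooled power is 10.3%. A Cochran-Mantel-Haenszel (CMH) test stratified by cohort reaches only 14.1%, so stratifying does not rescue this rate. In the HPR cohort the NPR rate is the complement of the HPR rate and adds nothing.

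Direction in the NPR cohort: a harmful shift of +30 gives Φ((208 − 180)/35) − Φ((85 − 180)/35) = 78.8% − 0.3% = 78.5%. So 30 PRU of benefit (83.5%) and 30 PRU of harm (78.5%) both lower the rate from 92.0%.

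**HPR rate (above 208), if pooled.** Expected rates are 41.5% and 26.8%.

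| Test | Pooled, balanced | Pooled, allocation ignoring cohort | Stratified, balanced | Stratified, allocation ignoring cohort |
|---|---|---|---|---|
| Uncorrected (chi-square; CMH) | 16.0% | 27.4% | 62.4% | 60.9% |
| Exact (Fisher; stratified exact) | 9.1% | 20.2% | 48% | 51% |

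Balanced figures are enumerated and figures for allocation ignoring cohort are simulated, except that both stratified exact figures are simulated. With continuity correction, CMH is 43.4% (balanced).

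**HPR rate, if tested within cohorts.** HPR cohort: chi-square 51.9%, Fisher 38.1%. NPR cohort: 2.1% and 0.4%, because only 23 × 4.9% = 1.1 and 23 × 0.6% = 0.1 HPR patients are expected.

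**Sensitivity.**
- Assumed regression to the mean, from placebo means of 235 and 150 to 225 and 165: for the HPR rate, pooled chi-square is 39% to 65% and CMH 70% to 77%.
- At an NPR-cohort mean of 165, the NPR rate in that cohort rises slightly: Φ(43/35) − Φ(−80/35) = 87.9% on placebo, Φ(73/35) − Φ(−50/35) = 90.5% on evolocumab. With the HPR mean at 225, the same enumeration gives pooled NPR-rate power of 43%.
- Baseline truncated at the entry limits plus an assumed within-patient SD of 0 to 45 PRU: for the HPR rate, pooled tests have 13–43% power and uncorrected CMH 37–98%, with stratified above pooled in every case.

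**The case against.** The strongest objection is that the cohorts will not be pooled. The end point, the distributions and the sample sizes are all set by cohort, and group there means treatment arm. Comparing arms within each cohort is the natural reading, and no pooled analysis is described. This stands. A reader might infer that the plan commits to a pooled HPR-rate test with 9–27% power where 61–62% was available. The documents do not support that: pooling is not excluded, but it is not stated. The contrast also sets an exact test at one end against an uncorrected CMH at the other, and assumes no regression to the mean.

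Nor is stratification always better than the within-HPR-cohort test. CMH falls to 41.6% if the NPR cohort's HPR rate does not change, below the 51.9% for chi-square in the HPR cohort alone. Part of its advantage in the base case is test size: under the null with balanced arms, CMH rejects 5.1% of the time, within-HPR chi-square 2.6% and pooled chi-square 0.0%.

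It can also be said that HPR and NPR percentages by arm give the share below 85 by subtraction. That is true if both are reported by cohort, but the plan does not say they will be, and the NPR-rate p-value would still carry no direction.

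Finally, the rates are secondary and no power is claimed for them. This stands and limits the weight of the point.

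**Conclusion.** The concern holds as a minor point about a secondary analysis. Its firm part is the NPR rate. Under the plan's own figures the assumed benefit raises it in one cohort and lowers it in the other, leaving about 4% power pooled with balanced arms. In the NPR cohort, benefit and harm of equal size both lower it. The exact percentages rest on normal day-30 PRU at the plan's means and SDs. With a higher NPR-cohort mean the rate rises slightly instead and pooled power is larger, so even the sign of the change depends on where that cohort sits.

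The HPR-rate part is conditional. Only if the cohorts are pooled does the unstratified test lose substantial power, and the gap narrows under regression to the mean. Tested within cohorts, the HPR-cohort comparison is reasonable as planned.

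The primary PRU ANCOVA is untouched and shows the direction of mean PRU. A reader might infer an inflated false-positive rate from ignoring cohort; the calculations show no material inflation (pooled chi-square 5.3% and Fisher 3.1% with allocation ignoring cohort, both near 0.0% when balanced).

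**What to change.** In the Statistical analysis plan:

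- State that the day-30 VerifyNow HPR rate (PRU above 208) is reported by arm within each cohort, with the Fisher or chi-square test in the HPR cohort, and say which of the two will be used.
- Stratify any overall HPR-rate comparison by entry cohort, using CMH or a stratified exact test, and name the version.
- Replace the NPR-rate test with a table of PRU above 208, 85–208 and below 85, by arm within each cohort.

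This costs one or two sentences and uses data already collected. The downside is slightly more analysis. The overall stratified test also assumes a common direction of effect across cohorts, so it should accompany the per-cohort results and not replace them.
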